8.6.2. Sensitivity Analyses of the Primary Efficacy Results

Primary efficacy analysis will be based on the ITT population with a sensitivity analyses for efficacy based on the PP and completers populations. A second analysis using the ITT population with subject-reported rather than expert-confirmed events will also be conducted.

In addition, there will be 2 sensitivity analyses to examine the effect of missing data.

1. A missing data sensitivity analysis will be conducted in which observed data post study drug discontinuation are included in event rate determination. The estimand for this analysis is referred to as the de facto estimand. Details on the determination of the event rate are provided in Section 6.8.1.
2. A missing data sensitivity analysis will be conducted in which observed data post study drug discontinuation are used in combination with imputed data for subjects who discontinue study treatment prior to the end of Part 1 and do not continue to provide event information. The method of imputation will depend upon whether the data are considered missing at random or not missing at random. Details on the imputation methodology are provided in Section 6.8.1.

A forest plot will be provided to visually compare the results obtained using these methods of sensitivity analyses to the primary efficacy result.

Sensitivity analyses will also be conducted for the combined study.

8.7. Analysis of the Secondary Efficacy Endpoints

Analysis of the secondary efficacy endpoints will be conducted for the combined study.

8.7.1. Angioedema Quality of Life (Total and Domain Scores)

CFB in AE-QoL questionnaire at Week 24 (total score) is a secondary endpoint for Part 1. Durability in AE-QoL questionnaire scores is a secondary endpoint for Part 2.

The actual and change from baseline domain and total scores will be summarized by visit and treatment. For Part 1, changes from baseline in AE-QoL will be assessed with a MMRM model with fixed effects for treatment, baseline event rate, baseline AE-QoL, visit, and a visit by treatment interaction and a random effect for subject. An unstructured covariance structure will be used. The estimated treatment difference comparing each active treatment to placebo at each post-baseline visit (Weeks 4, 6, 12, 18, and 24) will be displayed together with the 95% CI and the associated p-value. Least squares means (LSM) for each visit will also be presented with the standard error and the number of subjects contributing to the LSM. Total and domain scores will be listed for each subject and visit. The responses to the individual AE-QoL questions will also be listed.

Figures of mean actual and change from baseline AE-QoL total and domain scores will be produced with one line per treatment group. In addition, a cumulative distribution plot of AE-QoL Total Score at Week 24 will be provided.

Final analyses at the end of Part 2 will also include data from visits at Weeks 28, 32, 36, 48, and 52. Summaries will be updated to include the additional information. An additional descriptive summary of change from Week 24 will be provided for Part 2 visits for subjects originally randomized to placebo treatment.

A summary and analysis of the number and percent of subjects with at least a six-point decrease (Minimum Clinically Important Difference [MCID]) in total AE-QoL score will be performed by visit for Part 1. The summary will be repeated at the end of Part 2. The analysis for Part 1 will be based on a logistic model with response of achievement of the MCID (yes/no), baseline event rate and baseline AE-QoL total score as covariates and a fixed effect for treatment.

8.7.2. Number and Proportion of Days with Angioedema Symptoms

The number and proportion of days with angioedema symptoms through 24 weeks is a secondary endpoint for Part 1. The number and proportion of days with angioedema symptoms is also a secondary endpoint for Part 2. Definitions of the endpoints are provided in Section [6.7.5.3](#).

For Part 1, the number and proportion of days with angioedema symptoms through Week 24 will be determined. Both the number and proportion of days will be summarized. The proportion of days with angioedema symptoms through Week 24 will be analyzed using an ANCOVA model with baseline event rate as a covariate and treatment included as a fixed effect. The estimated treatment difference comparing each active treatment to placebo will be displayed together with the 95% CI and the associated p-value. LSMs will be presented with the standard error and the number of subjects contributing to the LSM. The number and proportion of days with angioedema symptoms will be listed for each subject. A similar analysis will be conducted based on the effective dosing period, beginning on Day 8 and continuing through Week 24.

Final analyses at the end of Part 2 will include a summary of the number and proportion of days with angioedema symptoms through Week 52 for those subjects originally randomized to active treatment and a summary through adjusted Week 24 for active treatment for subjects originally randomized to placebo. Only subjects who received at least one dose of study treatment in Part 2 of the study will be included in this summary. The subject listing will be updated to include the number and proportion of days with angioedema symptoms through the end of the study. The number and proportion of days with angioedema symptoms during Part 3 of the study will be reported separately from Part 2.

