Japan has limited statistical power. A supplemental analysis will combine data from this study with data from Study BCX7353-302. The primary efficacy endpoint in Study BCX7353-302 is the monthly investigator-confirmed angioedema event rate in the entire treatment period (Day 1 [post dose] to Day 168) in the ITT population. The angioedema event rate and the treatment comparisons between each BCX7353 dose and placebo in the rate of investigator- or expert-confirmed HAE angioedema events during the entire dosing period will be analyzed using a negative binomial regression model. The number of investigator- or expert-confirmed angioedema events will be included as the dependent variable, the treatment will be included as a fixed effect, the stratification variable (baseline angioedema event rate) will be included as a covariate, and the logarithm of duration on treatment will be included as an offset variable. The estimated rate of angioedema event for each treatment group, the treatment differences expressed as the angioedema event rate ratio (BCX7353 over placebo rate ratio), and their associated 95% confidence intervals will be provided from the negative binomial regression model. Monthly will be defined as 4 weeks. Descriptive summaries, figures, and listings will be produced for efficacy endpoints of interest. Safety data analyses will be conducted using data from the current study alone. The safety analyses will be analyzed separately for Part 1 alone; a later data analysis will evaluate long-term safety data for the current study. Safety endpoints that will be summarized include, at a minimum, the number and proportion of subjects 1) with a TEAE; 2) who discontinue BCX7353 due to a TEAE 3) who experience a TESAE; 4) who experience a Grade 3 or 4 TEAE; and 5) who experience a treatment-emergent Grade 3 or 4 laboratory abnormality. In addition, the proportion of subjects with treatment-emergent, treatment-related AEs consistent with a drug rash will also be summarized.

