13.4.4.1. Primary Efficacy Analysis

The primary efficacy endpoint is the rate of expert-confirmed angioedema events during dosing in the entire treatment period of Part 1 of the current study.

The sample size considered feasible for enrollment in Japan has limited statistical power. Therefore, a supplemental statistical analysis will be conducted using the combined monthly angioedema event rate (investigator-confirmed attacks in Study BCX7353-302 and expert-confirmed events in Study BCX7353-301) in the entire treatment period in the ITT population. The angioedema event rate and the treatment comparisons between each BCX7353 dose and placebo in the rate of investigator- or expert-confirmed angioedema events during the entire dosing period will be analyzed using a negative binomial regression model. The number of investigator- or expert-confirmed angioedema events will be included as the dependent variable, the treatment will be included as a fixed effect, the stratification variable (baseline monthly angioedema event rate) will be included as a covariate, and the logarithm of duration on treatment will be included as an offset variable. The estimated rate of angioedema events for each treatment group, the treatment differences expressed as the angioedema event rate ratio (BCX7353 over placebo rate ratio), and their associated 95% confidence intervals (CIs) will be provided from the negative binomial regression model. Monthly will be defined as 4 weeks.

The potential impact of missing data on the primary efficacy outcome will be explored. Sensitivity analyses will be conducted to support the primary analysis. This will include analyses based on subjects who completed the study and on those in the PP population.

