The sample size considered feasible for enrollment in Japan has limited statistical power. Therefore, a supplemental statistical analysis will be conducted in the same manner as above using the combined data from Studies 301 and 302. The combined rate of HAE events will utilize investigator-confirmed attacks from Study 302 and expert-confirmed events from Study 301.

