8.6. Analysis of the Primary Efficacy Endpoint

8.6.1. Primary Efficacy Analysis

The primary efficacy endpoint for Part 1 of the study is the rate of expert-confirmed HAE events during dosing in the entire 24-week dosing period during Part 1 (Day 1 to first dose of Part 2). The first dose in Part 2 is expected on Day 169. The primary efficacy analysis will be produced using the ITT population. The estimand will be based on data from subjects who are on study treatment and this analysis will not include data post treatment discontinuation.

The number of expert-confirmed HAE events for Part 1 will be analyzed by treatment group using appropriate descriptive statistics for the confirmed event rate (expressed as events/month) based on the 24-week dosing period or until study treatment discontinuation, if applicable. An additional summary of confirmed event rate by month, including CFB event rate and percentage CFB event rate by month, will be produced. The primary efficacy analysis will be conducted using Part 1 data and the primary efficacy endpoints will be summarized and listed by Part 1 treatment group.

The angioedema event rate and the treatment comparisons between each BCX7353 dose and placebo in the rate of expert-confirmed angioedema events during the entire dosing period will be analyzed using a negative binomial regression model. The number of expert-confirmed angioedema events will be included as the dependent variable, the treatment will be included as a fixed effect, the stratification variable (baseline monthly angioedema event rate) and study (for the combined study analysis) will be included as covariates, and the logarithm of duration on treatment will be included as an offset variable. The estimated rate of angioedema events for each treatment group, the treatment differences expressed as the angioedema event rate ratio (BCX7353 over placebo rate ratio), and their associated 95% confidence intervals (CIs) will be provided from the negative binomial regression model. Monthly will be defined as 28 days.

The percentage reduction from placebo will be calculated for each dose as:

$$\text{Percentage rate reduction} = (1 - \text{event rate ratio}) * 100 = (1 - \frac{R_A}{R_P}) * 100$$

Where R_P is the estimated event rate for Placebo treatment and R_A is the estimated event rate for Active treatment.

Example SAS pseudo-code for the negative binomial regression analysis is as follows:

```
proc genmod data = datasetname;  

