  class trt01p /param=glm;  
  model ecevents = trt01p blatk /dist=negbin link=log offset=logdurtrt;  
run;
```

All statistical tests will be two-sided. Multiplicity adjustments for Part 1 analyses for the two dose groups are discussed in Section 8.5 along with handling of testing of multiple endpoints.

Plots of mean confirmed event rate by month and scatter plots of baseline event rate vs. 24-week event rate will be produced with a different color for each treatment. Plots of mean event rate per month will be updated to include the Part 2 data at the end of Part 2. Adjusted subject-reported event rate data per month will be plotted separately for Part 3, as Part 3 does not include expert confirmation of events. A scatterplot will be produced for the difference between the baseline confirmed event rate and the confirmed event rate for Part 1 vs. the baseline confirmed event rate. This scatterplot will also be produced by gender. A plot of confirmed events by study day for Part 1 will be presented for individual subjects by treatment group and will display the length of each event and will include the use of on-demand medication. A plot of individual event rates showing the baseline and the Part 1 confirmed event rate will be presented by treatment group. A plot of individual event rates showing the baseline and confirmed event rates for each month will be presented by treatment group.

The sample size considered feasible for enrollment in Japan has limited statistical power. Therefore, a supplemental statistical analysis will be conducted in the same manner as above using the combined monthly angioedema event rate (investigator-confirmed attacks in Study 302 and expert-confirmed events in Study 301) in the entire treatment period in the ITT population.

The relationship of selected baseline characteristics with the expert-confirmed events will be explored using an appropriate model-building method for Part 1.

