15. CHANGES FROM PROTOCOL-SPECIFIED ANALYSES

The following changes from protocol-specified analyses are as follows:

- The definition of the screen failure population has changed from subjects not dispensed treatment to those who are not randomized and are reported as screen failures in the eCRF.
- The definition of the PP population has been altered to include $\geq 85\%$ treatment compliance as an inclusion requirement.
- Part 1 is defined as Day 1 to first dose of Part 2 rather than Day 1 through Day 168.
- The entire dosing period for Part 1 is defined as Day 1 to first dose of Part 2 rather than Day 1 through Day 168 and Day 1 through Day 168 + 24 hours.
- The negative binomial regression model will be used instead of the Poisson regression model for all applicable analyses. The Poisson regression that was originally proposed is a special case of the negative binomial regression model. For Study 302, the required assumptions of the Poisson model were not met, and the negative binomial model was used instead. For this reason and because there will be a combined analysis of the current study with Study 302, the negative binomial model results for the current study will be provided.

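### Combined 301+302 analysis: the symptom-days, AE-QoL and responder models list no study term, and the symptom-days ANCOVA leaves out its own baseline

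*SAP*

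**What the plan says.** The combined analysis is supplemental to the 301-alone primary analysis. SAP 8.5 says that "a supplemental statistical analysis will be conducted in the same manner as above using the combined data from Studies 301 and 302", and for the secondary endpoints SAP 8.7 states: "Analysis of the secondary efficacy endpoints will be conducted for the combined study".

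The model terms are given endpoint by endpoint:

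- **Primary event rate (8.6.1).** Negative binomial with treatment, baseline event rate, a duration offset, "and study (for the combined study analysis) will be included as covariates".
- **Proportion of symptom days (8.7.2), second in the hierarchy.** It "will be analyzed using an ANCOVA model with baseline event rate as a covariate and treatment included as a fixed effect". No other term is listed.
- **Effective-period event rate (8.7.3) and medication rate (8.7.4).** Both refer back to the primary model. Neither names study.
- **AE-QoL (8.7.1).** The mixed model lists treatment, baseline event rate, baseline AE-QoL, visit, visit by treatment, and subject. The MCID logistic lists treatment, baseline event rate and baseline AE-QoL.
- **Responders (8.8.2).** Logistic with treatment and baseline event rate, and Fisher's exact test as a fallback when responders are very few.

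SAP 7.9 summarises the proportion of symptom days in the baseline period, and the combined output list includes it (14.1.3.7.1.C). SAP 6.7.5.3 defines the endpoint for the dosing period and gives no formula for the baseline version.

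**The concern.** Subjects were randomised within each study, so study is the natural stratum when the two are pooled. The SAP accepts this for the primary endpoint. It then lists full term sets for four other models without study, and nothing in those sections brings it in by reference. A between-study shift in symptom days is plausible: only days within confirmed events count, and events are confirmed by an independent expert in 301 and by the investigator in 302. SAP 5.3 treats the two as equivalent.

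The ANCOVA is also out of line on baseline adjustment. The AE-QoL model adjusts for its own baseline; the symptom-days model does not, although that baseline comes from diary data already collected.

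What is at stake is precision at a gate. In the combined hierarchy a dose must succeed on symptom days before its effective-period rate and AE-QoL can be tested, and the two doses progress separately.

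**Working it through.** **The plan's own figures.** The only power figures (SAP 4.3) concern the event rate: difference 0.6, SD 0.5, two-sided 5%. A noncentral t calculation gives 60.8% for 8 per group (stated 61%) and 99.96% for 40 per group (stated above 99%), so both reproduce. Neither bears on symptom days, for which the documents give no SD, effect size or correlation. The values of r and d below are therefore assumptions.

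**Sample size.** Study 302 randomised 121 (protocol 5.3.1). Study 301 planned 24 (protocol 8.1) and had 19 dosed at the April 2020 review (protocol 5.3.3). So N = 24 + 121 = 145, or 19 + 121 = 140. The written ANCOVA uses 4 parameters (intercept, two treatment terms, baseline event rate), leaving df = 141 or 136.

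**Adding baseline symptom days.** Let r be its partial correlation with the outcome, given treatment and baseline event rate. Charging one degree of freedom:

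SE factor = sqrt(1 - r²) × sqrt(df / (df - 1)), with sqrt(141/140) = 1.0036.

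| r | SE change, N = 145 |
|---|---|
| 0 | +0.36% |
| 0.1 | -0.15% |
| 0.2 | -1.67% |
| 0.3 | -4.27% |
| 0.4 | -8.02% |

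The term pays for itself once r exceeds sqrt(1/df): 0.084 (df 141) or 0.086 (df 136).

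**Adding study.** Let p be the 301 share and d the between-study shift in residual SDs. Omitting study adds p(1 - p)d² to the residual variance, so

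SE factor = 1 / sqrt(1 + p(1 - p)d²) × sqrt(df / (df - 1)).

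| d | 24 of 145, p(1 - p) = 0.1381 | 19 of 140, p(1 - p) = 0.1173 |
|---|---|---|
| 0 | +0.36% | +0.37% |
| 0.25 | -0.07% | 0.00% |
| 0.5 | -1.33% | -1.07% |

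Break-even is d = sqrt(1 / ((df - 1)p(1 - p))) = 0.227 or 0.251.

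**Both terms uninformative.** sqrt(141/139) gives +0.72%.

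**Bias from omitting study.** Bias = d × (301 share in the active arm minus 301 share in the placebo arm). Take d = 0.5 and the treated 302 arms of 41/40/39 (110 mg, 150 mg, placebo). The splits of 19 are illustrative, because the documents do not give the 301 arm counts. The larger of the two dose comparisons is shown.

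| 301 split | 301 share per arm | Bias (SD) |
|---|---|---|
| 8/8/8 | 0.1633 / 0.1667 / 0.1702 | 0.0035 |
| 7/6/6 | 0.1458 / 0.1304 / 0.1333 | 0.006 |
| 6/7/6 | 0.1277 / 0.1489 / 0.1333 | 0.008 |
| 6/6/7 | 0.1277 / 0.1304 / 0.1522 | 0.012 |

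**301 alone, for contrast.** One extra term costs sqrt(20/19) = +2.60% with 24 subjects or sqrt(15/14) = +3.51% with 19, and breaks even only at r = 0.22 or 0.26.

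**The case against.** The best case for leaving the plan alone has three parts, and each stands in part.

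- **The gain may be small.** Baseline event rate is already in the model, and baseline symptom days come from the same run-in events, possibly only two per subject. A low r is quite possible. That limits the benefit but not the argument, because the loss at r = 0 is 0.4%.
- **The choice comes late.** Study 302 was already reported and supplies 121 of 140 to 145 subjects (83 to 86%). Changing the covariates of a gatekeeping test now costs some credibility. This is the real downside and it shapes the fix.
- **The logistic models behave differently.** Adding a prognostic covariate changes the conditional odds ratio and can raise its standard error, so the 0.4% figure does not carry over to them.

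A reader might also infer more than the documents support:

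- *That the example GENMOD code contradicts its own text.* The line "model ecevents = trt01p blatk /dist=negbin link=log offset=logdurtrt" has no study term, but it is labelled an example and fits the 301-alone model, where study is constant.
- *That study is an undeclared departure from the protocol.* Protocol 13.4.4.1 has "the stratification variable (baseline monthly angioedema event rate) will be included as a covariate, and the logarithm of duration on treatment", its synopsis has "the stratification variable (baseline angioedema event rate) will be included as a covariate", and neither names study. SAP 15 ("The following changes from protocol-specified analyses are as follows") does not list it. But SAP 2 cites protocol versions only up to Version 5 of August 2019, while the protocol in hand reports an April 2020 review. SAP 15 also records a move away from Poisson, whereas this protocol already specifies negative binomial. Whether anything is missing from that list cannot be judged here, and protocol 13.4 leaves detailed methods to the SAP.
- *That the medication-rate and effective-period models omit study.* Both refer to the primary model and can be read as inheriting it.
- *That the health-outcome models are affected.* SAP 9.1 to 9.3 describe no combined run, and the SAP's combined output lists contain no EQ-5D-5L, TSQM or WPAI display.

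**Conclusion.** The point holds as a modest improvement to the supplemental combined analysis. The symptom-days ANCOVA, AE-QoL mixed model, MCID logistic and responder logistic list no study term although the combined primary model has one. The ANCOVA also leaves out a baseline that the SAP already summarises.

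The written models are valid under randomisation within study. It would be wrong to read this as a bias or type I error problem: even a 0.5 SD shift between studies moves a treatment difference by no more than 0.012 SD in the splits examined. The case for study is one rule across combined models. The case for baseline symptom days is precision at the second gate, and its size cannot be derived from the documents. Over assumed r from 0 to 0.4 the net change in standard error runs from a 0.4% loss to an 8.0% gain.

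**What to change.** For combined 301+302 runs only:

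1. **Study term.** Add study to the models in SAP 8.7.1 (mixed model and MCID logistic), 8.7.2 and 8.8.2. State that 8.7.3 and 8.7.4 carry it over from 8.6.1. Exempt subgroups in which study does not vary, and responder analyses where sparse cells trigger Fisher's exact test. Name study in the SAP synopsis.
2. **Baseline covariate.** Define the baseline proportion of symptom days in SAP 6.7.5.3: days from screening to first dose with at least one symptom during a confirmed baseline event, divided by the SAP 6.6.1 denominator (first-dose date minus screening date plus 1). Add it to the 8.7.2 ANCOVA, and report the ANCOVA as now written as a sensitivity analysis.
3. **Timing.** Record both in a dated SAP amendment before 301 Part 1 is unblinded. If that has already happened, run the added covariates only as a labelled sensitivity analysis.

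Leave the 301-alone models unchanged, since one extra term there costs 2.6 to 3.5% of the standard error.

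Cost: one definition and a few sentences, with no new data. Each term that explains nothing costs about 0.4% of the ANCOVA standard error (0.7% for both); the cost in the logistic models has not been computed. The covariates would be chosen with the 302 results known, which is why the dated record and the retained written model matter.
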